5.4 Treatment blinding

Patients, investigator staff, persons performing the assessments and data analysts will remain blind to the identity of the treatment from the time of randomization until database lock, using the following methods: (1) Randomization data are kept strictly confidential until the time of unblinding, and will not be accessible by anyone else involved in the study with the exception of the IWRS provider generating the randomization code, members of the DMC and the independent biostatistician assigned to the DMC. (2) The identity of the treatments will be concealed by the use of investigational treatments that are identical in packaging, labeling, and schedule of administration, appearance, taste and odor.

Confidential

Unblinding will only occur in the case of patient emergencies (see Section 5.5.11) and at the conclusion of the study.

5.5 Treating the patient

5.5.1 Patient numbering

Each patient is uniquely identified by a Subject Number which is composed by the 4-digit site number (e.g., 0501, 0502 etc.) assigned by Novartis and a 5-digist sequential number assigned by the investigator (e.g., 00001, 00002, etc.). Hence a 9 -digit study patient identification number, e.g., 050100001. Once assigned to a patient, the Subject Number will not be reused.

Upon signing the informed consent form, the patient is assigned the next sequential number by the investigator. The investigator or his/her staff will contact the IWRS and provide the assigned patient study identification number along with the requested identifying information for the patient to register them into the IWRS. The site will enter this number on the electronic case report form (eCRF) in the electronic data capture system (EDC).

5.5.2 Dispensing the investigational and comparator treatment

Each study site will be supplied by Novartis with investigational and comparator treatment in packaging of identical appearance. Each hospital will be provided a kit for Day 1 of treatment, from which all patients will be provided their first 2 doses. This kit will include dose levels 1 and 2 and their matching placebos. Since the first day of treatment is placebo only for patients randomized to the sacubitril/valsartan arm in order to facilitate the required 36-hour washout, the bottles assigned for the sacubitril/valsartan treatment arm will all contain placebos. Patients will receive their first 2 doses from the centralized hospital supply. The third dose of treatment will be provided from the patient supply that will be sent home with the patient upon discharge.

The investigational and control treatment packaging will have a 2 -part label. A unique randomization number is printed on each part of this label which corresponds to one of the 2 treatment arms and a dose level. Investigator staff will identify the investigational treatment package(s) to dispense to the patient by contacting the IWRS and obtaining the medication number(s). Immediately before dispensing the package to the patient, investigator staff will detach the outer part of the label from the packaging and affix it to the source document (Drug Label Form) for that patient's unique subject number.

5.5.3 Handling of study treatment

5.5.3.1 Handling of investigational and comparator treatment

Investigational and comparator treatment must be received by a designated person at the study site, handled and stored safely and properly, and kept in a secured location to which only the investigator and designees have access. Upon receipt, all investigational and comparator treatment should be stored according to the instructions specified on the labels. Clinical supplies are to be dispensed only in accordance with the protocol. Medication labels will include storage conditions but no information about the patient except for the medication number.

Confidential

The investigator must maintain an accurate record of the shipment and dispensing of investigational and comparator treatment in a drug accountability log. Monitoring of drug accountability will be performed by field monitors during site visits or remotely and at the completion of the trial. Patients will be asked to return all unused investigational or comparator treatment and packaging at the end of the study or at the time of discontinuation of treatment.

At the conclusion of the study, and as appropriate during the course of the study, the investigator will return all unused investigational and comparator treatment, packaging, drug labels, and a copy of the completed drug accountability log according to the instructions provided by Novartis or its agents.

5.5.3.2 Handling of other study treatment

Each study site will be supplied by Novartis with open -label sacubitril/valsartan for the 4week open-label follow up period. The IWRS will need to be called to receive drug shipments prior to dispensing.

The open-label sacubitril/valsartan packaging will have a 2-part label. Investigator staff will identify the treatment package(s) to dispense to the patient by contacting the IWRS and obtaining the medication number(s). Immediately before dispensing the package to the patient, investigator staff will detach the outer part of the label from the packaging and affix it to the source document (Drug Label Form) for that patient's unique subject number.

Open-label sacubitril/valsartan treatment must be received by a designated person at the study site, handled and stored safely and properly, and kept in a secured location to which only the investigator and designees have access. Upon receipt, all open-label sacubitril/valsartan treatment should be stored according to the instructions specified on the labels. Clinical supplies are to be dispensed only in accordance with the protocol. Medication labels will include storage conditions but no information about the patient except for the medication number.

The investigator must maintain an accurate record of the shipment and dispensing of openlabel sacubitril/valsartan treatment in a drug accountability log. Monitoring of drug accountability will be performed by field monitors during site visits or remotely and at the completion of the study. Patients will be asked to return all unused open-label treatment and packaging at the end of the study or at the time of discontinuation of treatment.

At the conclusion of the study, and as appropriate during the course of the study, the investigator will return all unused open-label treatment, packaging, drug labels, and a copy of the completed drug accountability log according to the instructions provided by Novartis or its agents.

5.5.4 Instructions for prescribing and taking study treatment

All medication for the duration of the study will be provided by Novartis. Eligible patients will be randomized via IWRS to either sacubitril/valsartan or enalapril. Patients randomized to the sacubitril/valsartan arm will receive sacubitril/valsartan matching placebo for the first day of treatment to fulfill the required 36 -hour wash-out period (in addition to enalapril matching placebo). Patients randomized to enalapril will not require a washout and will receive active treatment on the first day of treatment, in addition to sacubitril/valsartan matching placebo. The first day of dosing will be provided from a centralized hospital supply containing dose levels 1 and 2 and matching placebos.

From the second day of treatment (third dose), patients will be provided with sufficient medication to last until the next scheduled visit. In order to adequately blind the study, patients will be required to take a total of two tablets (one tablet from the sacubitril/valsartan / sacubitril/valsartan matching placebo pack and one tablet from the enalapril/enalapril matching placebo pack) twice a day for the duration of the study.

Initial dose at randomization will be determined by systolic blood pressure (SBP).

- All patients with a systolic blood pressure (SBP) of ≥100 to ≤120 mm Hg will start at Dose level #1 (2.5 mg Enalapril or 24/26 mg sacubitril/valsartan, BID).
- Patients with a SBP \geq 120 mm Hg will start at dose level #2 (5 mg enalapril or 49/51 mg sacubitril/valsartan, BID).
- Patients will be titrated to the next dose level at Weeks 1 and 2 (Visits 3 and 4) with the goal of reaching the target dose for dose level #3 (10 mg enalapril or 97/103 mg sacubitril/valsartan, BID) by week 2 (Visit 4).
- Patients should be titrated to the next dose level at week 1 only if their SBP is >110 mm Hg and at week 2 if their SBP is > 100 mm Hg.

Table 5-3	Dose titration schedule based on SBP			
Visit	Previous dose level	Systolic Blood pressure mm Hg*	Start/remain/tit rate to: Dose level #	
Baseline (Visit 2)	N/A	≥ 100	1	
	N/A	≥120	2	
1 Week (Visit 3)**	1	<110	1	
		≥110	2	
	2	<110	2	
	2	≥110	3	
2 weeks (Visit 4)	1	<100	1	
	I	≥100	2	
	2	<100	2	
	2	≥100	3	

Dose titration will proceed according to the following table:

Novartis Amended Protocol Version 02 (Clean) Page 36 Protocol No. CLCZ696BUS01

Visit	Previous dose level	Systolic Blood pressure mm Hg*	Start/remain/tit rate to: Dose level #
4 Weeks (Visit 5)	1	<100	1
	1	≥100	2
	2	<100	2
	2	≥100	3
6 Weeks (Visit 6)	1	<100	1
	1	≥100	2
	2	<100	2
	2	≥100	3

**Up titration may be done prior to the week 1 visit for patients who were started at dose level 1 who were previously on high dose RAS blockade (>10 mg enalapril total daily dose or > 160 mg valsartan total daily dose or equivalent doses of other ACEi or ARB).

Confidential

Dose adjustments to lower dose levels may be made at any time at both scheduled and unscheduled visits only if indicated for blood pressure control/tolerability reasons.

Study medication should be taken with a glass of water with or without food. If the patient misses taking any study drug dose, he/she should take it as soon as possible, unless it is almost time for the following scheduled dose. In this case, the patient should skip the missed dose and return back to his/her regular study drug administration schedule.

All dosage prescribed and dispensed to the patient and all dose changes during the study must be recorded in the IWRS and on the Dosage Administration Record eCRF.

The investigator should promote compliance by instructing the patient to take the study treatment exactly as prescribed and by stating that compliance is necessary for the patient's safety and the validity of the study. The patient should be instructed to contact the investigator if he/she is unable to take the study treatment as prescribed for any reason.

All patients that complete 8 weeks of treatment will proceed with a 4 -week follow up on open-label sacubitril/valsartan. All patients will have the wash out in order to maintain the blinding of the core study. To facilitate this washout, patients should take their final dose of study drug on the morning of their week 8 visit and then begin open label sacubitril/valsartan after 36 hours in the evening of week 8 visit + one day. All patients will start open label treatment on sacubitril/valsartan at their final dosing level during double blind treatment. However, at an investigator's judgement, starting dose may be adjusted by one dose level up or down.

The intent of the open-label phase is to have the patients up-titrated to the desired dose level #3 (200 mg sacubitril/valsartan) based on clinical need and investigator judgement.

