5.1.1 Investigational and control treatment

Table 5-1 Investigational and comparator treatment

All eligible patients will be randomized to receive either sacubitril/valsartan or enalapril. The following study treatment will be provided:

Treatment	Minimum dose	Maximum dose	Frequency	Admin. Route
sacubitril/valsartan	24/26 mg	97/103 mg	BID	oral
sacubitril/valsartan matching placebo				oral
Enalapril	2.5 mg	10 mg	BID	oral
Enalapril matching placebo				oral

Dose Level	sacubitril/valsartan	Enalapril
1	24/26 mg BID	2.5 mg BID
2	49/51 mg BID	5.0 mg BID
3	97/103 mg BID	10 mg BID

Both sacubitril/valsartan and enalapril and their matching placebos will be packaged and labeled by the sponsor in accordance with the US Code of Federal Regulation s governing handling of investigational treatments, and will be dispensed by the study physician.

Matching placebo will also be needed for sacubitril/valsartan combination tablet and matching placebo for the enalapril for the first day of treatment to allow for the 36-hour washout required for patients randomized to the sacubitril/valsartan treatment arm.

Each participating hospital will be provided with a central supply kit containing dose levels 1 and 2 and their matching placebos. Bottles will be numbere d and assigned via an Interactive Web Response System (IWRS). On the day of randomization (visit 2), the IWRS system will assign both a hospital kit and a patient kit.

Treatment for the day of randomization will be provided to the patients from the hospital kit.

Treatment for the second day of dosing onward will be provided from the patient kit which patients will take home upon discharge.

Patients not tolerating the target dose of sacubitril/valsartan 97/103 mg bid or enalapril 10 mg bid will be titrated down to the lower dose level (including active medication and matching placebos), at the investigator's discretion, based on the defined safety and tolerability criteria.

Sacubitril/valsartan dose or enalapril dose levels may be increased to the targeted desired dose level #3 of 97/103mg twice daily or enalapril 10 BID on an every 2 week basis or earlier if based on clinical need and investigator judgement.

Patients not tolerating the target dose level #3 of sacubitril/valsartan 200 mg BID or enalapril 10 mg BID will be titrated down to the lower dose level (including active medication and matching placebos), at the investigator's discretion, based on the defined safety and tolerability criteria.

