5.3 Treatment assignment, randomization

The randomization numbers will be generated using the following procedure to ensure that treatment assignment is unbiased and concealed from patients and investigator staff. A randomization list will be produced by or under the responsibility of Novartis D rug Supply

Management using a validated system that automates the random assignment of treatment arms to randomization numbers in the specified ratio.

Confidential

Eligible patients will be randomized no earlier than 24 hours after presentation at the hospital and no later than within ten days of admission, while still hospitalized, via IWRS to one of the treatment arms. The investigator or his/her delegate will contact the IWRS after confirming that the patient fulfills all the study entry criteria. The IWRS will assign a randomization number to the patient, which will be used to link the patient to a treatment arm and will specify which bottle from the centralized hospital supply the patient will be dosed for the first day and a unique medication number for the first package of investigational treatment to be dispensed to the patient. The initial dose will be determined by the patient's blood pressure at the time of the call to the IWRS.

The randomization numbers will be generated using the following procedure to ensu re that treatment assignment is unbiased and concealed from patients and investigator staff. A patient randomization list will be produced by the IWRS provider using a validated system that automates the random assignment of patient numbers to randomization numbers. These randomization numbers are linked to the different treatment arms, which in turn are linked to medication numbers. A separate medication list will be produced by or under the responsibility of Novartis Drug Supply Management using a validat ed system that automates the random assignment of medication numbers to packs containing the investigational drug(s).

Initial dose at randomization will be determined by systolic blood pressure (SBP). See Table 5-3.

Dose adjustments to lower dose levels may be made at any time at both scheduled and unscheduled visit only if clinically indicated for blood pressure control/tolerability reasons. Dose adjustments to increase dose levels may be made at any time at both scheduled and unscheduled visits based on clinical need or investigator judgement.

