5.5.5 Permitted dose adjustments and interruptions of study treatment

Every attempt should be made to maintain patients on the target study drug dose level for as long a duration as possible throughout the study. If, however, in the opinion of the investigator, a patient is unable to tolerate the protocol-specified target dose, the investigator should consider whether dose adjustments of concomitant medications may rectify the situation before reducing the dose of study treatment. If adjustment of the concomitant medications is not possible or does not alleviate the side effects of concern, the investigator may down-titrate the dose of the study drug to the previous dose level. If needed, the study drug may be stopped completely, but the patient should continue to attend the study visits and be followed until the completion of the study. Patients may restart their current dose of study drug following an interruption of treatment, based on investigator judgment.

Study drug dose level adjustments should be mainly based on overall safety and tolerability with special focus on hyperkalemia, symptomatic hypotension

Adjustment of study drug dose level

If necessary, the patient may be down-titrated to the next lower dose level. The patient may continue receiving the lower dose level for a recommended period of 1 to a maximum of 4 weeks. Re-challenge to titrate back up to the target dose level should be attempted at 2 weeks. It must be noted that the desired dose of study medication is the highest dose (dose level #3), but patient tolerability and safety must be taken into account.

If the tolerability issues are not alleviated despite down -titration by one dose level, the investigator may lower the study drug dose further to the next lower level for 1 to a maximum of 4 weeks, up to temporary withdrawal of the study drug. Again, once stable, the patient should be re-challenged with up-titration to the next higher dose level in an attempt to bring back the patient gradually to the target study drug dose level (dose level #3). The investigator may choose the next dose level for down - or up-titration according to his or her clinical judgment. The IWRS should be contacted to register any changes in the patient's study drug dose level, including in cases of temporary and permanent withdrawal of the study drug, and to obtain the medication numbers of the study drug supplies required for the new study drug dose level.

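### Section 5.5.4 gives two starting doses at SBP exactly 120 mm Hg, and its Week 1 and Week 2 cut-offs differ from Table 5-3 at exactly 110 and 100

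*Protocol*

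**What the plan says.** Protocol section 5.5.4 sets the starting dose in two bullets. The first reads "All patients with a systolic blood pressure (SBP) of ≥100 to ≤120 mm Hg will start at Dose level #1". The second, for SBP at or above 120, reads "120 mm Hg will start at dose level #2 (5 mg enalapril or 49/51 mg sacubitril/valsartan, BID". The fourth bullet allows an increase "at week 1 only if their SBP is >110 mm Hg and at week 2 if their SBP is > 100 mm Hg".

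The same section then gives Table 5-3, titled "Dose titration schedule based on SBP". Its baseline rows give level 1 at ≥100 and level 2 at ≥120. At Week 1 it keeps the level below 110 and raises it at ≥110. At Weeks 2, 4 and 6 it keeps the level below 100 and raises it at ≥100.

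The sentence that introduces Table 5-3 makes the table the titration schedule. Section 5.3 refers the initial dose to the same table and adds: "The initial dose will be determined by the patient's blood pressure at the time of the call to the IWRS". SAP section 2.4.1 plans a summary of dose level and titration by visit and SBP, using the cut-offs of the titration schedule.

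**The concern.** The bullets and the table are both operative dosing instructions, and at certain exact pressures they cannot both be followed. The 120 case is a conflict within the bullets themselves: both say the patient will start at the stated level, and the levels differ. It concerns the starting dose of an inpatient who has only just been stabilized after acute decompensation.

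At Week 1 and Week 2 the conflict is between text and table. A site that reads only the bullets holds the dose at exactly 110 or 100; a site that reads only the table raises it. The SAP summary uses the schedule's cut-offs, so a patient held at exactly 110 in line with the bullet would be shown as having met the cut-off without being up-titrated.

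**Working it through.** No figure in the plan needs reproducing. The check applies both sets of rules to each whole-number SBP (99 to 125 for the starting dose, 90 to 130 for titration) and lists where they disagree. The table's ≥120 row is taken to override its open-ended ≥100 row.

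| Decision | SBP | 5.5.4 bullets | Table 5-3 |
|---|---|---|---|
| Starting level | 120 | level 1 (100 ≤ 120 ≤ 120) and level 2 (120 ≥ 120) | level 2 |
| Week 1 | 110 | hold (110 is not > 110) | raise (110 ≥ 110) |
| Week 2 | 100 | hold (100 is not > 100) | raise (100 ≥ 100) |

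The rules agree at every other value tested.

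**Dose difference at SBP 120.** From the dose-level table in section 5.1.1: enalapril 5/2.5 = 2; sacubitril component 49/24 = 2.04. The gap is about twofold. In the sacubitril/valsartan arm the first two doses are placebo (section 5.5.2), so there the level first matters at the third dose.

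**How many patients.** The documents give no SBP distribution, so this part rests on an assumption: SBP is normal with mean 110, 115, 120 or 125 and SD 12, 15 or 18, the same at each visit. With recording step w (1 or 2 mm Hg), the share at exactly v is

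P(v − w/2 < SBP < v + w/2),

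divided at entry by P(SBP > 100 − w/2), because entry requires SBP ≥100. Example for entry, mean 120, SD 12, w = 1: 0.0332 / 0.956 = 0.0348, and 0.0348 × 882 = 31.

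| Exact value | w = 1: share | of 882 | w = 2: share | of 882 |
|---|---|---|---|---|
| 120 at entry | 0.0231–0.0348 | 20–31 | 0.0461–0.0692 | 41–61 |
| 110 at Week 1 | 0.0152–0.0332 | 13–29 | 0.0305–0.0664 | 27–59 |
| 100 at Week 2 | 0.0038–0.0235 | 3–21 | 0.0076–0.0470 | 7–41 |

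The Week 1 and Week 2 rows assume that all 882 attend. They overstate the numbers, because patients off drug, or already at level 3 by Week 2, face no such decision.

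**The case against.** The strongest reply is that the protocol already says what to do. It makes Table 5-3 the titration schedule and the reference for the initial dose, and section 3.1 bases titration on blood pressure at the visit. With the table as the rule, 120 gives level 2, and both 110 and 100 lead to an increase. This stands, and it is why the table should be kept and the bullets changed. It does not remove the contradiction, because the bullets remain in the same section with mandatory wording.

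A reader might infer more: that nothing decides between the table and investigator judgement, since section 5.1.1 allows increases "on an every 2 week basis or earlier if based on clinical need and investigator judgement" and section 5.3 says that adjustments to "increase dose levels may be made at any time at both scheduled and unscheduled visits based on clinical need or investigator judgement". The documents do not support that reading. A default schedule with room for judgement is ordinary titration design. Section 5.5.5 also lets the investigator keep a patient at level 1 or 2 with reasons in the eCRF, and says "The investigator may choose the next dose level for down - or up-titration according to his or her clinical judgment". A sentence on when judgement may override a row that keeps the level would be useful, but its absence cannot be confirmed: the note to the asterisk on the SBP column is not in the text reviewed, nor is the Treatment Manual given to sites.

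Two further replies stand in part. The signs at Weeks 1 and 2 could be reading errors, since an underlined > can lose its bar. That would not explain the 120 overlap, where the first bullet shows ≤: losing a bar cannot turn < into ≤. And the IWRS receives the blood pressure at the randomization call, so it may already settle the 120 case in practice; the documents do not say how.

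**Conclusion.** The dosing instructions contradict each other at three exact values. The overlap at 120 is clear in the text as read. The differences at 110 and 100 depend on confirming the two signs on the original PDF.

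The consequence is small: about a twofold difference in starting dose for patients at exactly 120, and one titration step at exactly 110 or 100. The patient counts rest wholly on the assumed SBP distributions and recording step.

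A reader might chain the three values in one patient (120, then 110, then 100) and arrive at a fourfold gap, level 1 against level 3. That needs three exact readings in a row and the lower of two conflicting bullets, so it is not a fair measure of the problem. Nor is bias in the NT-proBNP result shown: the same rules apply in both blinded arms, the primary model contains treatment and log baseline but no dose level, no per-protocol exclusion in SAP section 5.6 concerns titration, and the SAP dose summary is descriptive.

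**What to change.** - First bullet of 5.5.4: change the range to ≥100 to <120 mm Hg.
- Table 5-3, baseline row for level 1: give it the same upper limit, ≥100 to <120.
- Fourth bullet of 5.5.4: change the cut-offs to ≥110 at Week 1 and ≥100 at Week 2, once the signs are confirmed on the original.
- Confirm that the IWRS assigns level 2 at SBP 120.

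Section 11.1 requires a written, approved amendment for any protocol change, so these edits belong in the next amendment made for other reasons. The cost is the wording, a site notification and one IWRS check. No new data, visits or SAP change are needed, since the SAP already uses the schedule's cut-offs, and investigator discretion under 5.1.1, 5.3 and 5.5.5 is left as it is.
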